At baseline, pattern separation task will also be completed where participants will be shown pictures of everyday objects and asked to indicate if the picture is old, new, or similar which provides an assessment of memory performance. The delay between first presentation and repeated presentation of a lure or repeated image will vary. Images remained on the screen for 2 seconds, followed by a 500 millisecond inter-stimulus interval. Participants will view a total of 324 images.

Self-Report Measures. Demographic questionnaire - The Depression Anxiety and Stress Scale (DASS-21) - The PTSD Checklist - Civilian Version (PCL) - The McGill Pain Questionnaire - The Brief Pain Inventory (BPI) - The World Health Organization Disability Assessment Schedule II (WHODAS-II) - The World Health Organization-Quality of Life (WHO-QOL) - The Military to Civilian Questionnaire (M2C-Q) - Medication usage and therapy involvement - Brief Religious Coping Scale (R-COPE) - Chronic Pain Acceptance Questionnaire (CPAQ) - Cognitive Fusion Questionnaire (CFQ-13) - Acceptance and Action Questionnaire (AAQ-II) - Experiences Questionnaire (EQ) - Chronic Pain Values Inventory (CPVI) - Pain Intensity - Committed Action Questionnaire (CAQ) - Trauma Recovery Scale, Part III (TRS) - Impact of Events Scale (IES) - Social Network Index (SNI) - UCLA Loneliness Scale - Moral Injury Scale (MIS)

Treatment: Pilot 1. If the assessment confirms the presence of psychopathology and mTBI, the patient will be invited to attend a workshop called ACT on Life based on Acceptance and Commitment Training (ACT). 10 Veterans will complete this ACT on Life Workshop.

Workshop: Patients in the ACT condition will attend a 1-day group workshop. Each ACT group will be held at MEDVAMC, include 5-8 patients, and will last 6 hours. The ACT group will be conducted by the PI and a doctoral level psychologist or advanced doctoral student. The intervention includes: 1) Behavioral Change Training (2 hours) involving a) teaching patients how to recognize ineffective patterns of behavior and habits, b) exploring

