and setting life goals and goals related to mental and physical health, and c) promoting effective and committed actions to achieve these goals despite the urge to do otherwise; 2) Mindfulness and Acceptance Training (2 hours) emphasizing new ways of managing troubling thoughts, feelings, and physical sensations (e.g., learning how to recognize, and develop cognitive distance from unhelpful thoughts such as „I can’t take this pain anymore, or „I am not good enough,) and learning how to face willingly experiences that cannot be changed; and 3) Education about PTSD, TBI, and chronic pain conditions (2 hours).

A total of 10 Veterans will complete the ACT on life Workshop in Pilot 1. These 10 Veterans will provide feedback about the workshop at 2-weeks and 12-week follow-up visits. The feedback will be used to make modifications to the ACT on Life workshop so that it is more Veteran-centric. All following eligible Veterans will be part of Pilot 2.

Pilot 2. If the assessment confirms the presence of psychopathology and mTBI, the patient will be randomized into either the ACT workshop or treatment as usual condition (TAU). The ACT workshop will be similar to that described above but will incorporate feedback from Veteran who completed Pilot 1 and any additional edits from the expert team.

An individualized phone booster session will take place 3-4 weeks following the workshop. During the phone call, we will ask participants if they are using the strategies taught, troubleshoot difficulties, and review some of the main concepts taught in the workshop. The booster session interview guide is attached.

Follow-up: At 2 weeks, 6 weeks, and 12 weeks, following the workshop, patients in both the ACT and Treatment as Usual (TAU) groups will complete assessments over the phone or in-person.

The follow-up assessments are expected to take 1 hour and are attached.

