At the 2-week follow-up, the following self-report measures will be completed: Chronic Pain Acceptance Questionnaire (CPAQ) - Chronic Pain Values Inventory (CPVI) - Acceptance and Action Questionnaire (AAQ-II) - Experiences Questionnaire (EQ) - Group Climate Questionnaire (GCQ) - Client Satisfaction Questionnaire (CSQ) - Feedback about workshop - Pain Intensity Scale - Therapy and medication usage - Committed Action Questionnaire (CAQ) - Cognitive Fusion Questionnaire (CFQ-13) - Brief Religious Coping Scale (R-COPE) - Trauma Recovery Scale, Part III (TRS) - Impact of Events Scale (IES) - Social Network Index (SNI) - UCLA Loneliness Scale .

Feedback about the workshop will also be obtained from the Veterans.

At the 6-week follow-up, the following self-report measures will be completed: Chronic Pain Acceptance Questionnaire (CPAQ) - Chronic Pain Values Inventory (CPVI) - Acceptance and Action Questionnaire (AAQ-II) - Experiences Questionnaire (EQ) - Pain Intensity Scale - Therapy and medication usage -Committed Action Questionnaire (CAQ) - Cognitive Fusion Questionnaire (CFQ-13) - Brief Religious Coping Scale (R-COPE) - Trauma Recovery Scale, Part III (TRS) - Impact of Events Scale (IES) - Social Network

Index (SNI) - UCLA Loneliness Scale

At the 12-week follow-up, the following will be completed: Clinical Interviews. The Structured Clinical Interview for DSM-IV Axis I Disorders (SCID-IV) - the Clinician Administered PTSD Scale (CAPS). Feedback about the workshop will also be obtained from the Veterans.

The pattern separation task will again be repeated at the 12 week follow-up.

Self-Report Measures. The Depression Anxiety and Stress Scale (DASS-21) -The PTSD CheckList ζ Civilian Version (PCL) - The McGill Pain Questionnaire - The Brief Pain Inventory (BPI) - The World Health Organization Disability Assessment Schedule II (WHODAS-II) - The World Health Organization-Quality of Life (WHO-QOL) - The Military to Civilian Questionnaire (M2C-Q) - Medication usage and therapy involvement - Brief Religious Coping Scale (R-COPE) - Chronic Pain Acceptance Questionnaire (CPAQ) - Cognitive Fusion Questionnaire (CFQ-13) - Acceptance and Action Questionnaire (AAQ-II) - Experiences Questionnaire (EQ) - Chronic Pain Values Inventory (CPVI) - Pain Intensity - Committed Action Questionnaire (CAQ) - Trauma Recovery Scale, Part III (TRS) - Impact of Events Scale (IES) - Social Network Index (SNI) - UCLA Loneliness Scale.

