Provide a description of your plan for data analysis. State the types of comparisons you plan (e.g. comparison of means, comparison of proportions, regressions, analysis of variance). Which is the PRIMARY comparison/analysis? How will the analyses proposed relate to the primary purposes of your study?

Frequency data will be gathered on the number of veterans screened for participation and the number willing to participate in the study, the number of Veterans who are not eligible to participate and the reasons for lack of eligibility will also be tracked to identify the proportion of Veterans who may have difficulties and may be in need of an intervention.

We hypothesize that at 3-month follow-up, Veterans randomized to ACT on Life will experience greater improvements in Quality of life (WHO-QOL), functioning (WHODAS-II), distress (DASS-21), and pain-interference (BPI) compared to the TAU group. Data collected at baseline, 2-, 6- and 12-weeks follow-up for each of the aforementioned outcomes of interest will be compared between the groups using a generalized linear mixed model (GLMM) that can accommodate repeated measures over time and missing data due to loss to follow-up or missed interviews. Based on our previous experience with this population and the high retention rates for 1-day ACT trials, we anticipate a 10% loss-to-follow-up rate at the 12-week evaluation. The GLMM model for each outcome will include group, week (continuous outcome) and group by week interaction as the predictors. The influence of key demographic variables (e.g., age, rural/urban, gender) on the outcomes of interest will also be explored by adding these variables as predictors to the linear models.

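### The G2 model does not adjust for the baseline score: on the two visits listed for the main outcomes it is a valid change-score test, but usually less precise than an adjusted one (minor)

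*Combined protocol and SAP*

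**What the plan says.** G2 sets a comparative hypothesis: "We hypothesize that at 3-month follow-up, Veterans randomized to ACT on Life will experience greater improvements" on quality of life (WHO-QOL), functioning (WHODAS-II), distress (DASS-21) and pain interference (BPI), relative to treatment as usual (TAU). The method is a generalized linear mixed model, for which the plan says: "Data collected at baseline, 2-, 6- and 12-weeks follow-up for each of the aforementioned outcomes of interest will be compared between the groups". Its fixed part is given as: "The GLMM model for each outcome will include group, week (continuous outcome) and group by week interaction as the predictors". The only further predictors are demographic variables, added for exploration. The baseline score is not named as a covariate, and nothing constrains the two arms to a common baseline mean. On attrition, "we anticipate a 10% loss-to-follow-up rate at the 12-week evaluation".

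The schedule in F2 differs from G2. The baseline list contains all four outcomes (for example "The Brief Pain Inventory (BPI) - The World Health Organization Disability Assessment Schedule II (WHODAS-II) - The World Health Organization-Quality of Life (WHO-QOL", with DASS-21 earlier in the same list), and so does the 12-week list. The lists that begin "At the 2-week follow-up, the following self-report measures will be completed: Chronic Pain Acceptance Questionnaire (CPAQ" and "At the 6-week follow-up, the following self-report measures will be completed: Chronic Pain Acceptance Questionnaire (CPAQ" contain none of the four. F2 also says of the follow-up forms: "The follow-up assessments are expected to take 1 hour and are attached". Those attachments are not in the text reviewed, but the F2 lists are explicit.

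G1 (Sample Size) randomises 2:1 to obtain preliminary efficacy data, describes earlier ACT effects against TAU as moderate, and accepts low power because this is a pilot.

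**The concern.** Randomised arms have the same expected baseline mean. A model with a free group term at week 0 does not use that fact. It estimates the baseline difference and subtracts it in full, so the noise in the baseline scores passes into the treatment estimate. Adjusting for baseline, or fitting one common baseline mean, removes only as much of the chance difference as the correlation supports.

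What is at stake is the width of the week-12 intervals in a trial that calls itself underpowered, when the score needed to narrow them is already collected.

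The schedule conflict matters because it decides what the model estimates. With two visits, a linear week term is harmless. With four, the interaction becomes a straight-line slope, and G2 names no week-12 contrast to match its 3-month hypothesis.

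**Working it through.** **The plan's own figure.** G1 claims 80% power for Cohen's d above 1 at the 5% level. With the 30 Veterans of Section D, split 20:10, the detectable effect (two-sided, normal approximation) is (1.960 + 0.842) × √(1/20 + 1/10) = 1.09, in line with G1. With G1's total of 80, less 10 in Pilot 1, 70 are randomised (about 47:23) and the value is 0.71. The figure therefore fits 30 randomised, not 70. That is a separate matter, but it is why both sizes appear below.

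**Inputs.** From the documents: 2:1 allocation, 5% level and 10% loss, giving 42:21 completers (63 of 70) or 18:9 (27 of 30). Assumed: two-sided test, effect 0.5 in week-12 SD units, correlation r between baseline and week 12 of 0.3, 0.5 or 0.7, and k = week-12 SD divided by baseline SD.

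**Step 1: what the planned test is on two visits.** Fitting a random-intercept model to complete two-visit data gave 12 × interaction = 0.6563 (SE 0.2010). A regression of the change score on group gave the same estimate and SE. Simulated type I error was 0.047-0.052 for the change score and 0.046-0.053 with adjustment, so both are valid.

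**Step 2: variance per patient, week-12 SD = 1.**
- Change score: 1 + 1/k² − 2r/k, which is 2(1 − r) when k = 1.
- Baseline-adjusted: 1 − r².
- Ratio at k = 1: (1 + r)/2, so the cuts are 35%, 25% and 15%.
- Estimating the covariate effect costs a factor 1 + 1/(N − 4) for chance imbalance. At N = 63 the cuts become 33.9%, 23.7% and 13.6%.
- Keeping all 70 baselines (7 without week 12), free against common baseline mean: 32.6%, 23.1% and 13.7%.

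**Step 3: power at 0.5 SD, k = 1 (noncentral t).** Ranges at 42:21 span the three versions in Step 2; those at 18:9 are completers without and with the imbalance factor.

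| r | 42:21 planned | 42:21 adjusted | 18:9 planned | 18:9 adjusted |
|---|---|---|---|---|
| 0.3 | 34-35% | 48-49% | 17% | 23% |
| 0.5 | 45-46% | 56-57% | 22% | 26-27% |
| 0.7 | 66-67% | 72-73% | 33% | 36-38% |

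For completers at r = 0.5 and 42:21, the SE is √(1.00 × (1/42 + 1/21)) = 0.267 planned and √(0.75 × (1/42 + 1/21)) = 0.231 adjusted. The 95% CI half-width falls from 0.53 to 0.46-0.47 SD. To gain as much by recruitment would take 1/0.763 = 1.31 to 1/0.75 = 1.33 times the sample, or 22-23 more than 70. At G1's rate of about 4 a month that is five to six months.

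**Step 4: unequal SDs, 42:21, r = 0.3, 0.5, 0.7.**
- k = 1.25: cuts of 22%, 11% and 2%, or 20%, 9% and 0.3% with the imbalance factor. Planned power is 40%, 52% and 72%; adjusted power is 48-49%, 56-57% and 72-73%.
- k = 0.8: cuts of 50%, 43% and 37% without the factor.
- At 18:9 with the factor, the cut is about −2% at k = 1.25 and r = 0.7. At k = 1 it is 1% at r = 0.9 and −2% at r = 0.95.

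**Step 5: only if four visits are analysed.** Weeks 0, 2, 6, 12 have mean 5 and sum of squares 84. Suppose the full effect is present from week 2 (0, 1, 1, 1) and correlation is equal between all visits. The fitted slope is 5/84, so 12 × slope = 0.71 of the true week-12 effect. The fitted group difference at week 0 is 0.75 − 5 × 5/84 = 0.45, so group + 12 × interaction = 1.17. If correlation decays to 0.5 over 12 weeks, the two values are 0.98 and 1.10. If the effect grows linearly, both are 1.00.

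**The case against.** The strongest reply is that nothing is broken. The planned test is valid and matches a hypothesis about greater improvement. Baseline is not ignored, because the interaction is itself a change from baseline. G1 openly accepts low power in a pilot meant to test feasibility. All of that stands and is why the point is minor. But the pilot label does not remove the comparative efficacy aim that G1 and G2 state.

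A second reply is that the change-score reading rests on F2's lists, whereas G2 says four visits. This is fair, and it is why the schedule must be settled first. If four visits are used, effects grow linearly and correlations are equal, the slope test is slightly more powerful than the adjusted week-12 contrast above r of about 0.71, where (144/84)(1 − r) = (1 + r)(1 − r). At 42:21 the slope test has 80.3% against 79.5% at r = 0.75, 88% against 87% at 0.8, and 95% against 94% at 0.85. Below that it is no better: 39% against 49% at 0.3, 51% against 57% at 0.5, and 73% each at 0.7.

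Third, the gain rests on a correlation and an SD ratio that the documents do not give. In the scenarios shown it runs from about −2% to 50% of the variance. That also stands; the losses are very small and confined to corners of the range.

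Finally, validity here assumes independent patients and a normal, identity-link model with within-patient correlation. G2 states neither link nor random effects, and the workshop is delivered in groups. Clustering by workshop is a separate issue, and baseline adjustment does not address it.

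**Conclusion.** The concern holds, as a minor one. As written, the G2 model neither conditions on the baseline score nor uses the shared baseline mean that randomisation provides. On the two visits F2 lists, its test is a valid comparison of mean change; the equality is exact with complete data.

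With equal SDs and correlations of 0.3 to 0.7, that costs about 14-35% of the variance at 42:21, or 6 to 14 percentage points of power at 0.5 SD. The gain from adjusting is larger if scores narrow by week 12. It is close to nil, or slightly negative in the smaller trial, if they widen and correlate highly, or if correlation is near 0.9 or above. Correlation, SD ratio and effect size are assumptions, so confidence in the exact size is moderate. The clear documentary fault is the conflict between F2 and G2 over when the four outcomes are measured.

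**What to change.** 1. Reconcile F2 with G2 on the visits at which WHO-QOL, WHODAS-II, DASS-21 and BPI are collected.
2. In G2, adjust for the baseline score of each outcome, either as a covariate for the week-12 value or by keeping baseline as a response with one common mean across arms (no group effect at week 0).
3. If more than two visits are analysed, enter week as categorical and name the ACT-minus-TAU difference at week 12, with its 95% CI, as the tested quantity for each outcome.

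This costs two or three sentences in G2 and no new data. The statistical price is the small imbalance term in the covariate version and, with four visits, the slight power loss under linear growth at high correlation.
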